6 SCHEDULE OF VISITS AND PROCEDURES: RETROSPECTIVE ARM

6.1 Waiver of Consent

In order to capture all eligible candidates in the retrospective arm, data will be captured under an IRB approved waiver of consent if sites obtain IRB approval to do so.

6.2 Consent for liver staging and long term follow-up

If participants can be contacted, they will be asked if they would consent to return for one study visit for current liver staging unless standard of care liver staging by Fibroscan or liver biopsy has been performed within 12 months. Each subject will provide informed consent prior to commencement of any study procedures according to ICH and Code of Federal Regulations (CFR). Each subject will be provided a copy of the signed informed consent form. The consent will also include approval to be contacted in the future by the NIH and/or co-investigators for additional longer term follow-up.

6.3 Time-points

Clinical data from day 0 (start of treatment), week 4, and end of treatment (week 12 or 24 depending on treatment duration) will be recorded in the Redcap database. Data will also be recorded at 3 months post treatment with DAA and again at 6 or more months post treatment with DAA. A complete list of study procedures to be captured is outlined in the Schedule of Events (Section 11)

7 SCHEDULE OF VISITS AND PROCEDURES: PROSPECTIVE ARM

Participants will be seen on each study visit at the enrolling center. A complete list of study procedures to be performed is in the Schedule of Events (Section 11).

7.1 Screening (Visit 1)

Each subject will provide informed consent prior to commencement of any study procedures according to ICH and Code of Federal Regulations (CFR). Each subject will be provided a copy of the signed informed consent form.

After a subject has provided informed consent, screening evaluations will be conducted and the investigator and other study personnel will determine if the subject is eligible for participation in the study. Screening will include a review of the medical history, inclusion/exclusion criteria, concomitant medications, physical examination, and blood tests. Screening tests that have been done as part of other studies or at an outside facility can be used if within the acceptable time frame (applicable lab tests within 56 days before enrollment). Some tests in the schedule of events allow the use of historic data to be used, such as the virology panel, HIV VL, CD4+ T-cell count, and HLA. These have been marked accordingly in the schedule of events.

Screening procedures do not need to be repeated within the 8 week screening window unless clinically indicated.

7.2 Liver Staging (Screening)

All pre-transplant subjects must have prior standard of care liver staging consistent with F4. All post-transplant subjects must have stage of liver disease documented within the prior year by standard of care liver staging methods.

7.3 Physical Examination, including vitals signs

All participants will have a physical visit for the final determination of protocol eligibility. In addition, participants will have a physical examination performed at the following time points: Day 0, week 4, week 12 and (if applicable) week 24 on treatment and at 6 months post treatment visits. A targeted physical exam will be performed on participants as needed for AE evaluation.

7.4 Starting SOF/LDV (Visit 2)

The participant will be started on SOF/LDV on Visit 2 (Day 0). For wait-listed patients, treatment start date should coincide with an anticipate time to transplant of at least 12 weeks (based on MELD score).

Blood will be drawn for standard of care labs and for research (HCV viral loads, drug level, immunologic studies, and for storage). For women with childbearing potential, a urine pregnancy test will be done on Day 0 and must be negative prior to dosing with study agent. The Day 0 procedures are summarized in Schedule of Events (Section 11).

7.5 Adverse event assessment and concomitant medications

At each visit, participants will be asked about their state of health and use of any concomitant medication since screening or the previous study visit. They will also be questioned about AEs and their adherence with study restrictions. In addition, participants will be seen at unscheduled visits for a grade 3 or 4 AE or any unexpected AE (adverse event) or potential toxicity.

7.6 Study Visits during treatment

All participants will be seen on days 0, weeks 4, and week 12 EOT, (or week 24 if treated for 24 wks).

- Weeks 4 (+/- 7 days)
- Week 12 [and 16, 20, 24 if applicable] (+/- 10 days)

Plasma HCV RNA will be obtained on each visit. Subjects who fail to achieve >2 log₁₀ HCV RNA drop at this time (unless >2 log drop would be below LLOQ) will be discontinued from therapy unless a review by the PI/Operations Committee determines otherwise.

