7.7 Week 12 or 24 Visit / End of Treatment Visit

Week 12 or 24 will mark the last dose of SOF/LDV to be administered. In addition, if a subject's participation terminates prior to end of treatment, the assessments may be performed at any end-of-treatment visit.

7.7.1 Liver Staging (End of Treatment):

All subjects will have end of treatment liver staging by the same method used to stage at screening.

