8.9 Criteria Requiring Discontinuation of SOF/LDV

Subjects will be considered treatment failures and will discontinue SOF/LDV if they meet any of the following criteria while taking study drugs:

- Plasma HCV RNA greater than LLOQ after 2 prior consecutive HCV RNA values less than the LLOQ
- Greater than a $1 \log_{10}$ increase in plasma HCV RNA from nadir
- Less than a $2 \log_{10}$ decline in HCV RNA after 4 weeks of treatment

If any of these should occur in a subject who is currently on study drugs, the subject should return within one week for a confirmatory test. If the confirmatory test also meets the same criteria, the subject will be considered a treatment failure and should be discontinued from therapy. Participants will be referred for other treatment options. The anticipated clinical impact of discontinuation should be discussed in advance if possible, particularly if discontinuation is thought to pose a risk to the overall clinical wellbeing of the subject. Those who are discontinued will continue to follow the general study schedule of assessments unless unwilling to do so, in which case they may be seen at least every 12 weeks for safety and research labs until the end of the study. Subjects will be followed closely for resolution of active laboratory abnormalities or adverse events that are considered related to the study agents prior to starting the revised schedule.

Subjects who meet any of the following laboratory criteria must stop all study medication(s):

- Any Grade 3 or greater rash associated with constitutional symptoms
- Any Grade 4 event assessed as possibly, probably, or definitely related to treatment with SOF or LDV

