11 SCHEDULE OF EVENTS

11.1 Schedule of Events Prospective Arm

	Screening	Day 0	Week 4	Week 12*	Week 24*	Day of Transplant	3M post treatment	6 M post treatment
			Month 1	Month 3	Month 6 if treated for 24 weeks	If transplant occurs post treatment with study drug	3 Months post treatment	6 Months or greater post treatment
History and Physical	X	X	X	X	X			X
Vital signs and Weight		X	X	X	X		X	X
Height	X							
Urinalysis		X						
Pregnancy Test: Urine		X ¹						
HBsAg	X							
Anti-HBc	X							
Virology Panel: (Historical only)								
Anti-HIV Ab	X							
Anti-HCV Ab	X							
HCV Genotype	X							
Plasma HCV RNA Levels		X	X	X	X		X	X
CD4+ T-cell count		X ²		X ²	X ²		X ²	X ²
HIV-1 RNA (bDNA or PCR)		X ²		X ²	X ²		X ²	X ²
Standard of care liver staging	X			X ³	X			
SERUM CHEMISTRY								
Alanine aminotransferase (ALT)		X	X	X	X		X	X
Albumin		X		X	X			X
Alkaline phosphatase		X	X	X	X		X	X
Aspartate aminotransferase (AST)		X	X	X	X		X	X
Bicarbonate (If on ARV regimen containing tenofovir)		X	X	X	X		X	X
Bilirubin, total, direct		X	X	X	X		X	X
Glucose (repeat during treatment, but only if abnormal at baseline)		X	X	X	X			
Phosphate (If on ARV regimen containing tenofovir)		X	X	X	X		X	X
Potassium (If on ARV regimen containing tenofovir)		X	X	X	X		X	X
Sodium		X	X	X	X		X	X
Serum Creatinine		X	X	X	X		X	X
HEMATOLOGY								
Hemoglobin		X		X	X			
Platelet Count		X		X	X			
White Blood Cell (WBC) Count		X		X	X			
Differential		X		X	X			
Neutrophils		X		X	X			
Lymphocytes		X		X	X			
INR		X		X	X			
RESEARCH								

Limited HCV Viral Kinetics		X	X	X	X			
Liver explant tissue (if achieved SVR)						X ⁴		
HLA	X ²							
Blood draw for immunologic studies		X	X	X	X		X	X
Paxgene DNA (6.5 ml)		X						
Paxgene RNA (2.5 ml)		X	X	X	X		X	
IL28B rs12979860 (run off Paxgene DNA sample)		X						
Blood for storage (8 cc SST serum, 6 cc EDTA)		X	X	X	X		X	X

*Subjects who are terminated early or who have early treatment discontinuation should have an end of treatment visit as soon as possible after therapy is stopped.

¹ Urine pregnancy test for females with childbearing potential must be negative on Day 0 prior to dosing with study agent

² documented historic results are acceptable. If not available, not required unless considered standard of care, or may be run on stored samples. For HIV-1 RNA and CD4+ T-cell counts, test results from primary care provider should be obtained per standard of care (every 3 months)

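### Section 7.6 and Schedule 11.1 disagree on Week 16 and Week 20 HCV RNA visits; on 11.1 the first stopping criterion in 8.9 cannot be met before the last-dose visit of a 24-week course

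*Combined protocol and SAP*

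**What the plan says.** Section 7.6 gives two visit lists for the prospective arm. Its lead sentence says "All participants will be seen on days 0, weeks 4, and week 12 EOT, (or week 24 if treated for 24 wks". The window bullet below it says "Week 12 [and 16, 20, 24 if applicable] (+/- 10 days". The section then adds "Plasma HCV RNA will be obtained on each visit", so a Week 16 or Week 20 visit would carry a viral load. What makes those weeks applicable is not defined.

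Section 7 says "A complete list of study procedures to be performed is in the Schedule of Events (Section 11". Schedule 11.1 has on-treatment columns for Day 0, Week 4, Week 12 and Week 24 only, the last headed "Month 6 if treated for 24 weeks". HCV RNA is marked in all four, and no footnote mentions Week 16 or 20.

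Section 8.9 sets three virologic criteria for stopping drug during treatment, each to be confirmed by a repeat test within a week. The first is a value above LLOQ "after 2 prior consecutive HCV RNA values less than the LLOQ". The second is a more than 1 log10 "increase in plasma HCV RNA from nadir". The third is a fall of less than 2 log10 after four weeks. Section 7.7 says "Week 12 or 24 will mark the last dose of SOF/LDV to be administered".

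**The concern.** A stopping rule works only if a test is scheduled when the rule could apply. A coordinator who treats 11.1 as complete would schedule nothing between Weeks 12 and 24. The first 8.9 criterion would then be assessable only when dosing is ending anyway. A patient whose virus returns after Week 12 could stay on a failing regimen until about Week 24. Section 13.1 lists resistance to both drug classes as a risk that may limit later treatment.

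The patients concerned are those treated past Week 12: recipients with cirrhosis, and pre-transplant patients not yet transplanted (Section 3.2). The unscheduled visits in 7.5 are for adverse events and toxicity, so they are not a planned substitute for viral-load monitoring.

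**Working it through.** The plan gives no figure of its own on this point, so the check compares the two schedules against the 8.9 rule.

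**Inputs**
- Nominal days: Week 12 = 84, Week 16 = 112, Week 20 = 140, Week 24 = 168.
- Visit window ±10 days (7.6); confirmation within 7 days (8.9); last dose at Week 24, taken as day 168 (7.7).
- Day 0 HCV RNA taken as quantifiable. This is an assumption, supported by the screening requirement of at least 1,000 IU/mL in 5.2.
- No unscheduled tests (assumption).

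**Gap between scheduled tests after Week 12**
- On 11.1: 168 − 84 = 84 days; shortest 158 − 94 = 64; longest 178 − 74 = 104.
- With the 7.6 visits: 112 − 84 = 28 days; shortest 102 − 94 = 8; longest 122 − 74 = 48.

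**Earliest point at which the first 8.9 criterion can be met.** Every pattern of below or not below LLOQ over the scheduled tests was listed, with Day 0 not below.

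| Scheduled tests (weeks) | Earliest trigger | Pattern needed |
|---|---|---|
| 11.1: 0, 4, 12, 24 | Week 24 | below at 4 and 12, above at 24 |
| 7.6: 0, 4, 12, 16, 20, 24 | Week 16 | below at 4 and 12, above at 16 |
| 12-week course: 0, 4, 12 | never at a scheduled visit | only one possible value below LLOQ (Week 4) precedes Week 12 |

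**Dosing days left after confirmation, full 24-week course**
- On 11.1, trigger at Week 24: 0 nominally. If the visit is 10 days early (day 158), confirmation comes the next day (day 159) and dosing still runs to day 168, then 168 − 159 = 9. With the full 7 days to confirm it is 168 − 165 = 3.
- With 7.6, trigger at Week 16: at least 168 − (112 + 7) = 49; at the late window edge at least 168 − (122 + 7) = 39.

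These are minimums because confirmation may come sooner than day 7. A pre-transplant patient whose course ends at transplant before Week 24 would have fewer days left.

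**Patient not yet below LLOQ at Week 4**
- On 11.1 only Week 12 can supply a value below LLOQ before Week 24, so the criterion cannot be met at a scheduled on-treatment test.
- With 7.6, Weeks 12 and 16 can both be below and Week 20 above. Days left are at least 168 − (140 + 7) = 21, and at the late edge at least 168 − (150 + 7) = 11.

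**The other criteria.** The less-than-2-log10 rule is first tested at Week 4 on either schedule. The more-than-1-log10 rise can act at Week 12 on either, but on 11.1 its next scheduled test is Week 24.

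**The case against.** The strongest reply is that the documents do not show which text is wrong. The 7.6 lead sentence, the examination times in 7.3, the viral-kinetics sampling in Section 12 and Schedule 11.1 all lack Weeks 16 and 20; a single bracketed list names them. A reader might infer that 11.1 plainly dropped two intended visits. The documents support only an inconsistency. Deleting the two weeks from the bullet would also reconcile the text and would add no visits. That stands as a point about intent. It does not remove the consequence, because that repair would leave the first criterion with essentially no effect in 24-week courses.

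The harm is also partly inferred. Section 13.1 says resistance may affect later options; it does not say that stopping at Week 16 instead of Week 24 would prevent it. Section 8.9 itself recognises that discontinuation can carry clinical risk. This limits how serious the point can be.

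Finally, if late reachability of the criterion were the whole defect, 12-week courses would share it. They do, but that does not arise from the conflict between 7.6 and 11.1, and the change proposed here does not alter it.

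**Conclusion.** The inconsistency is real and has a definite operational consequence. On 11.1 the first 8.9 criterion can first be met at Week 24, when nominally no dosing remains (up to about 9 days in the most favourable window case). With the 7.6 visits it can be met 8 weeks earlier. This rests on quantifiable HCV RNA at Day 0, no unscheduled tests and a full 24-week course. Sites that follow the 7.6 bullet do not have the problem.

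A reader might go further and infer that breakthrough would be missed or the efficacy result distorted. The documents do not support that: HCV RNA is still measured at Week 24 and after treatment, and SVR12, its exact confidence interval and the sample size do not depend on the two visits. Nor can the number of patients affected be estimated. The group is a subset of the 10 to 20 prospective patients, and no rate of breakthrough after Week 12 is given. Severity is minor to moderate; this is a cheap improvement.

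**What to change.** Add Week 16 and Week 20 columns to Schedule 11.1, marked as applying to patients treated beyond Week 12. Include plasma HCV RNA and the adverse-event and concomitant-medication questions that 7.5 already requires at every visit. Name both weeks in the 7.6 lead sentence, with the same condition. The 8.9 wording can stay as it is.

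The cost is a wording change plus two short visits per patient on a full 24-week course: at most 2 × 20 = 40 visits if all 20 prospective patients had such a course, all of them already named in 7.6. The downside is extra travel and blood draws for patients with advanced liver disease. If the sponsor does not intend these visits, the 7.6 bullet should be corrected instead, accepting that the first criterion then has essentially no effect before the end of a 24-week course.

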8.7 Dose Modifications/Toxicities

Maximal suppression of HCV replication is most likely accomplished by sustained delivery of antiviral agents at their current recommended doses. Dose reduction, however, would compromise this goal and predispose to the emergence of drug-resistant viral variants. Hence, no dose reduction will be allowed for SOF/LDV. If SOF/LDV is stopped due to toxicity, it must not be restarted.

If treatment with study drug is interrupted for \leq 5 consecutive days for reasons other than drug toxicity (such as discontinuation due to GFR $<$ 30), treatment can be reinitiated and the subject can remain in the trial. However, if treatment is interrupted for $>$ 5 days and/or if study drug is interrupted due to drug toxicity, treatment with study drug should be discontinued.

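### Sections 7.6 and 8.9 give different 2-log stopping rules for the prospective arm, and nothing says whether the exceptions in 7.6 survive 8.9

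*Combined protocol and SAP*

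**What the plan says.** Section 7.6 (Study Visits during treatment) lists the on-treatment visits, has HCV RNA drawn at each, and then stops patients who have not dropped by more than 2 log10. It gives two ways out. One is for patients whose baseline is too low to show such a drop: "unless >2 log drop would be below LLOQ) will be discontinued from therapy". The other is discretionary: "unless a review by the PI/Operations Committee determines otherwise".

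Section 8.9 (Criteria Requiring Discontinuation of SOF/LDV) opens with "Subjects will be considered treatment failures and will discontinue SOF/LDV if they meet any of the following criteria while taking study drugs". One listed criterion is less than a 2 log10 "decline in HCV RNA after 4 weeks of treatment". The patient returns within one week for a repeat, and then: "If the confirmatory test also meets the same criteria, the subject will be considered a treatment failure and should be discontinued from therapy". Neither the low-baseline exemption nor the committee override appears there.

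Two other sections bear on this. Section 8.8 says the drug is stopped when virologic criteria are met and lists no exception. Section 9.2 refers to 8.9 as the place where the criteria for stopping treatment are described. It does not mention 7.6.

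**The concern.** A site with a confirmed decline of less than 2 log10 has two instructions. Under 7.6 it may ask the PI/Operations Committee to keep the patient on drug, or treat a low-baseline patient as exempt. Under 8.9 it must stop the drug and record a treatment failure. Seven enrolling centers could handle and label identical results differently.

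At stake is whether a decompensated or transplanted patient stays on therapy. The protocol itself warns that relapse in these patients can be severe, and that stopping may put a patient's wellbeing at risk. The label matters too: 8.9 assigns treatment failure along with the stop, while 7.6 speaks only of the stop. For a patient continued by override, the plan does not say whether a treatment failure counts toward the enrollment pause in 16.1.1.

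**Working it through.** The plan gives no figure to reproduce here. The check is a comparison of the two rules, followed by arithmetic on how far the exemption reaches.

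**1. The two rules side by side**

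| Element | Section 7.6 | Section 8.9 |
|---|---|---|
| Threshold | drop must exceed 2 log10 | decline under 2 log10 fails |
| Time point | refers back to a list of visits; no single week named | after 4 weeks |
| Repeat test | none mentioned | within one week |
| Low-baseline exemption | yes | none |
| Committee override | yes | none |
| Labeled treatment failure | not mentioned | yes |

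A Week 4 value of exactly one hundredth of the Day 0 value is a drop of log10(100) = 2. That is not above 2, so it fails 7.6. It is not below 2, so it passes 8.9.

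**2. Other sections.** Sections 8.8, 8.10, 9.2, 16 and 16.1 contain neither the exemption nor the override. Section 9.2 names 8.9 as the home of the stopping criteria, but it is not a precedence clause and does not withdraw the 7.6 exceptions.

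**3. Reach of the override conflict.** It covers any prospective-arm patient (10, up to 20) with a confirmed decline under 2 log10, whatever the baseline. The documents give no rate for this.

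**4. Reach of the exemption conflict.** A 2-log drop falls below LLOQ when baseline / 100 < LLOQ, that is, when baseline < 100 × LLOQ. The largest decline that can be measured with a quantifiable result is log10(baseline / LLOQ). LLOQ has no numeric value in the documents, so a range is assumed:

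| Assumed LLOQ (IU/mL) | Exempt below (IU/mL) | Largest quantifiable decline from 1,000 |
|---|---|---|
| 10 | 1,000 | 2.00 |
| 12 | 1,200 | 1.92 |
| 15 | 1,500 | 1.82 |
| 25 | 2,500 | 1.60 |
| 43 | 4,300 | 1.37 |

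Entry requires at least one screening value of 1,000 IU/mL or more (Section 5.2). At an LLOQ of 10 or less, the exemption therefore reaches no baseline at or above that minimum. The minimum applies to screening, so a Day 0 value could be lower.

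**5. Illustration (invented values).** Day 0 of 1,400 and Week 4 of 200 IU/mL gives log10(1,400 / 200) = 0.85. With LLOQ between 15 and 25, Section 7.6 exempts this patient, since 1,400 is below 1,500. Under 8.9 any quantifiable repeat confirms the failure, because the largest quantifiable decline is log10(1,400 / 15) = 1.97 or log10(1,400 / 25) = 1.75, both under 2.

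**6. Downstream.** Section 16.1.1 pauses enrollment at 5 on-treatment failures among the first 20, so one disputed case is 1 of the 5. SVR12 is HCV RNA below LLOQ at 12 weeks after treatment (4.1.1). Patients who are discontinued stay on the assessment schedule unless unwilling, so the failure label does not itself set the SVR12 result.

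**The case against.** The best reply is that the sections can be read together. Section 8.9 supplies the week and the repeat test on which 7.6 is unspecific, so 7.6 may equally supply the exceptions on which 8.9 is silent. The virologic paragraph of 8.9 ends in softer language than the safety criteria that follow it, and it asks for the clinical impact to be discussed beforehand. Section 9.2 also tells the reader where the stopping criteria live. Finally, the documents describe rapid suppression with this regimen in coinfected patients, so Week 4 non-response may never occur.

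Part of this stands. The time point and repeat test can be combined without contradiction, and the numbers are small. The exceptions cannot be combined so easily: 8.9 opens with a mandatory stop, 8.8 repeats it, and a pointer to 8.9 favors the version without exceptions.

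Two stronger readings are tempting, and the documents do not support them.

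- *The stop cannot be undone in time.* A reader might set the limit in 8.7, which allows a restart only after an interruption of at most "5 consecutive days for reasons other than drug toxicity", against the committee's monthly call. But 8.9 makes the stop conditional on the repeat test, so drug continues through the confirmatory week. Section 7.6 does not tie the review to the monthly call, and Section 16 shows that the committee can hold calls at other times, at least for safety concerns.
- *Exempt patients need a new mandatory review.* A reader might note that the other virologic criteria in 8.9 miss a flat non-responder. One is "Plasma HCV RNA greater than LLOQ after 2 prior consecutive HCV RNA values less than the LLOQ". The other is more than a 1 log10 "increase in plasma HCV RNA from nadir", which means above 14,000 for a patient flat at 1,400, or above 2,000 for one who plateaus at 200. But neither section asks for such a review. The committee already looks at viral loads and treatment response monthly (Section 16), and items 5 and 6 of 9.2 let the investigator act in the patient's interest.

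**Conclusion.** The two sections state different rules. They differ on the low-baseline exemption, the committee override, the time point, the repeat test and the handling of a drop of exactly 2 log10. The first two matter most, because they decide whether the same confirmed result goes to a committee or leads to a mandatory stop and a recorded failure.

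The size is small: prospective arm only, few patients and possibly none. The exemption part rests on an assumed LLOQ. At 15 to 25 IU/mL it concerns baselines below 1,500 to 2,500; at 10 or less it reaches no one at or above the screening minimum. The override part needs no such assumption, but its frequency is unknown.

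A reader might infer that the primary efficacy result or the enrollment pause is compromised. The documents do not support that. SVR12 is measured HCV RNA, and the pause only triggers a data review and a decision on further enrollment. This is an inconsistency in an individual stopping rule. It should be corrected because it governs patient care, and it is no defect in the analysis.

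**What to change.** State one rule in Section 8.9, for example:

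> HCV RNA at or above LLOQ with less than 2 log10 decline from Day 0 at Week 4, confirmed by a repeat test within one week: treatment failure and discontinue, unless a 2-log drop from Day 0 would be below LLOQ or PI/Operations Committee review, held before drug is stopped, determines otherwise. A result <LLOQ never meets this criterion.

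Replace the stopping sentence in 7.6 with a cross-reference to 8.9. Section 16.1.1 then uses the 8.9 definition, under which a patient who is exempt or continued by the committee is not a treatment failure on this criterion. Section 8.8 needs no separate exception, since it refers to criteria that would now contain both.

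This keeps both protections already written into 7.6, settles the exactly-2-log case in favor of continuing, and adds no mandatory review for exempt patients. The cost is protocol wording in two sections. Sample size, visits and the SVR12 analysis do not change.
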